15.2.2. Vital Signs

Vital signs will include:

- SBP and DBP (mmHg) (controlled posture if possible);
- Heart rate (beats per minute [bmp]);
- Body temperature (°C or °F);
- Respiration rate (breaths per minute);
- Oxygen saturation by co-oximetry.

New or worsening clinically significant abnormalities following PICD signature will be reported as an AE.

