20. APPENDICES

APPENDIX 1: US PACKAGE INSERT OF PROVAYBLUETM

HIGHLIGHTS OF PRESCRIBING INFORMATION

These highlights do not include all the information needed to use (PROVAYBLUE®) safely and effectively. See full prescribing information for (PROVAYBLUE®).

PROVAYBLUE® (methylene blue) injection USP, for intravenous use

.....INDICATIONS AND USAGE

Initial U.S. Approval: 2016

PROVAYBLUE® (methylene blue) is an oxidation-reduction agent indicated for the treatment of pediatric and adult patients with acquired methemoglobinemia. This indication is approved under accelerated approval. Continued approval for this indication may be contingent upon

..... DOSAGE AND ADMINISTRATION

Administer 1 mg/kg intravenously over 5-30 minutes. (2.1)

verification of clinical benefit in subsequent trials. (1, 14)

 If methemoglobin level remains above 30% or if clinical symptoms persist, give a repeat dose of up to 1 mg/kg one hour after the first dose. (2.1)

.....DOSAGE FORMS AND STRENGTHS.....

50 mg/10 mL (5 mg/mL) single-dose ampule. (3)

.....CONTRAINDICATIONS.....

PROVAYBLUE® is contraindicated in the following conditions (4):

- Severe hypersensitivity to methylene blue
- Patients with glucose-6-phosphate dehydrogenase deficiency (G6PD) due to the risk of hemolytic anemia

......WARNINGS AND PRECAUTIONS....

 Hypersensitivity: If severe or life threatening allergic reaction occurs, discontinue PROVAYBLUE®, treat the allergic reaction, and monitor until signs and symptoms resolve (5.2)

- Lack of Effectiveness: Consider alternative treatments if there is no resolution of methemoglobinemia after 2 doses (2.1, 5.3)
- Hemolytic Anemia: Discontinue PROVAYBLUE® and transfuse (5.4)
- Interference with In-Vivo Monitoring Devices; Use methods other than pulse oximetry to assess oxygen saturation (5.5)
- Effects on Ability to Drive and Operate Machinery: Advise patients to refrain from these activities until neurologic and visual symptoms have resolved (5.6)

..... ADVERSE REACTIONS

The most commonly reported adverse reactions (>10%) are pain in extremity, chromaturia, dysgeusia, feeling hot, dizziness, hyperhidrosis, nausea, skin, discoloration and headache. (6.1)

To report SUSPECTED ADVERSE REACTIONS, contact American Regent at [name] or FDA at [name] or www.fda.gov/medwatch.

.....USE IN SPECIFIC POPULATIONS.....

- Pregnancy: Only use during pregnancy if the potential benefit justifies the potential risk to the fetus. (8.1)

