5.5 Interference with In Vivo Monitoring Devices

• Inaccurate Pulse Oximeter Readings

The presence of methylene blue in the blood may result in an underestimation of the oxygen saturation reading by pulse oximetry. If a measure of oxygen saturation is required during or shortly after infusion of PROVAYBLUE®, it is advisable to obtain an arterial blood sample for testing by an alternative method.

Bispectral index monitor

A fall in the Bispectral Index (BIS) has been reported following administration of methylene blue class products. If PROVAYBLUE® is administered during surgery, alternative methods for assessing the depth of anesthesia should be employed.

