- h. Vital signs will include: Systolic (SBP) and diastolic (DBP) blood pressure (mmHg), heart rate (beats per minute [bmp]), body temperature (°C or °F), respiration rate (breaths per minute), oxygen saturation by co-oximetry.
- i. If the patient is treated prior to consent, all available pre-treatment vital sign information should be retrieved where possible;
- j. Within 1 and 2 hours after the end of each ProvayBlueTM infusion (i.e. both Dose 1, Dose 2 and any additional dose if applicable).
- k. Additional (optional) parameters (for example blood gas) will be collected based on available data from patient standard of care.
- 1. Within 1 hour after the end of ProvayBlueTM infusion.
- m. If applicable (if the metHb level is acceptable within 1 hour after the end of Dose 1 ProvayBlueTM infusion, the repeat dose of ProvayBlueTM will not be needed).
- n. If applicable, in case of administration of additional doses of ProvayBlue at the discretion of the Investigator
- o. Collection of ECG data is mandatory at admission and approximately at 24 hours after the end of the last ProvayBlue™ infusion or just prior to discharge from the clinic if earlier than 24 hours. The collection of additional data will be based on available 12-lead ECG recordings performed as per patient standard of care as appropriate to determine general condition.
- p. ProvayBlueTM will be administered IV at a dose of 1 mg/kg over 5-30 minutes. If the methemoglobin level remains greater than 30% or if clinical signs and symptoms persist, a repeat dose of 1 mg/kg may be given 1 hour after the first dose. Depending on the clinical status of the patient, additional doses may be administered at the discretion of the Investigator. The data on these additional doses will be recorded in the study CRF.
- q. PK blood samples are to be drawn at the discretion of the Investigator. The suggested schedule of PK blood sampling is:
 - Approximately 1 hour after the end of each ProvayBlueTM infusion (i.e. Dose 1, Dose 2 and any additional dose if applicable);
 - Prior to Dose 2 (or any additional dose) ProvayBlue™ infusion (if applicable);
 - Approximately 24 hours post the end of the last ProvayBlue™ infusion, or just prior to discharge from the clinic if earlier than 24 hours.
- r. Collection of concomitant medications/medical procedures from PICD signature or the start of ProvayBlueTM treatment (whichever occurs sooner) until 10 to 15 days after the last administration of ProvayBlueTM;

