5.2.3. Summaries of Vital Signs Change from Baseline

A summary table will include VS measurement and change from baseline by relative time frame with descriptive statistics of sample size, mean, standard deviation, 2-sided 95% confidence intervals, quartiles (25% tile, 50% tile [median], and 75% tile), minimum, and maximum. The table will also include number (%) patients whose vital signs are within the normal range (Table 14.2.2.1). Number (%) patients who had at least 1 incidence of normal vital signs within the 2 hours following the completion of first dose ProvayBlueTM infusion will also be presented.

Change in SpO₂ will be assessed in 3 categories, based on $\pm 2\%$ rule as follows

- 1) Increased if the difference (postbaseline – baseline) is >2
- 2) No Change if the difference (postbaseline – baseline) is within ± 2
- 3) Decreased if the difference (postbaseline – baseline) is <2

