6.3. Other Safety Parameters

6.3.1. Changes in Other Blood Gas Tests

In addition to metHb, results from 11 other tests obtained via blood gas analysis with or without co-oximetry are collected (Table 5). Individual profiles of the co-oximetry results will be prepared (Figure 14.3.4), showing the observed value (Y) and relative time (X) to the first infusion. Data with assessment time will be included in the graphic display; all data (with and without assessment time) will be included in the data listing (Listing 16.2.12).

Table 5: Blood Gas Parameters of Interest

Parameter (Units)	Data Panel	
	Arterial Blood Gas	Co-Oximetry
1 Total Hemoglobin (g/dL)	Yes	Yes
2 SO ₂ /SaO ₂ (%)	No	Yes
3 C2CT (%)	No	Yes
4 OxyHb (%)	Yes	Yes
5 deoxyHb (%)	No	Yes
6 COHb (%)	No	Yes
7 pH	Yes	Yes
8 PaO ₂	Yes	No
9 PaCO ₂	Yes	No
10 HCO ₃	Yes	No
11 SaO ₂	Yes	No

Abbreviations: SO₂ = oxygen saturation; SaO₂ = arterial oxygen saturation; O₂CT = oxygen content; OxyHb = oxygenated hemoglobin; deoxyHb = deoxyhemoglobin; COHb = carboxyhemoglobin; pH = hydrogen ions (H⁺) in blood; PaO₂ = partial pressure of oxygen; PaCO₂ = partial pressure of carbon dioxide; HCO₃ = Bicarbonate.

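### SAP 5.2.3 classifies change in an undefined SpO₂; if this is pulse oximetry, the dye may push patients out of the Increased category

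*SAP*

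**What the plan says.** SAP 5.2.3 belongs to the efficacy chapter and describes the vital-signs summaries. It adds: "Change in SpO₂ will be assessed in 3 categories". The upper category reads "Increased if the difference (postbaseline – baseline) is >2" and the lower one reads "Decreased if the difference (postbaseline – baseline) is <2"; the middle category covers differences within ±2. SpO₂ is not in the SAP abbreviation list. Section 5.2.3 gives no device and does not say which post-dose reading is used. The summary table attached to that section is 14.2.2.1, whose period is baseline and the two hours after the first infusion.

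Protocol 15.2.2 lists the saturation vital sign as "Oxygen saturation by co-oximetry". The flow chart in protocol Appendix 2 agrees: "respiration rate (breaths per minute), oxygen saturation by co-oximetry". The SAP reproduces that chart, with the same footnote, as its Table 2.

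The US label in protocol Appendix 1, section 5.5, states: "The presence of methylene blue in the blood may result in an underestimation of the oxygen saturation reading by pulse oximetry". It advises an arterial sample tested by another method if saturation is needed while the infusion runs or soon after it. The label Highlights also steer users away from pulse oximetry.

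SAP 6.3.1, Table 5, lists SO₂/SaO₂ from co-oximetry and SaO₂ from arterial blood gas. These go to individual profiles and Listing 16.2.12, with no change categories and no summary table.

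**The concern.** The only saturation variable that the SAP sorts into better, unchanged or worse is the one whose source it leaves undefined. Its name points to a method that the product label cautions against in this setting. Any under-reading would come from the drug and would arise only after dosing, so it would enter the post-dose value but not the baseline. There is no control arm to offset it. A patient whose oxygenation improved could be tabulated as unchanged or worse.

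The pooled report is intended to satisfy a post-marketing requirement, so a count of Decreased patients in an efficacy table could be misread as lack of benefit or as harm. The registry relies largely on chart review, with timing set by local care. If its pulse-oximetry values and the interventional study's co-oximetry values share one field, the table would also mix two measures.

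**Working it through.** The plan states no figure on this point, so there is nothing to reproduce. The check has two parts: what is measured, and what the category rule does to a low reading.

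**1. Which measure is it?**

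- Protocol 15.2.2, protocol Appendix 2 and SAP Table 2 all specify co-oximetry.
- SAP 5.2.3 says SpO₂, while SAP Table 5 uses SO₂/SaO₂ and SaO₂ for co-oximetry and arterial blood gas.
- Usual notation and the different names in Table 5 favour pulse oximetry. No sentence in either document says so.

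**2. Does the period overlap?** Table 14.2.2.1 covers the two hours after the first infusion. The label's advice covers the infusion and shortly after it, with no limit in hours. The two overlap, although the label does not say for how long.

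**3. Effect of a low reading.** Let *t* be the true change in saturation and *a* the under-reading after dosing, both in percentage points. The observed change is *d* = *t* − *a*. Under the symmetric ±2 rule:

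- Increased needs *t* − *a* > 2, that is *t* > 2 + *a*.
- Decreased occurs when *t* − *a* < −2, that is *t* < *a* − 2.

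The documents give no value for *a*; the range 0 to 10 is my assumption. Each cell shows *d* and the resulting class.

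| True change *t* | *a* = 0 | *a* = 2 | *a* = 3 | *a* = 5 | *a* = 8 | *a* = 10 |
|---|---|---|---|---|---|---|
| 0 | 0, No Change | −2, No Change | −3, Decreased | −5, Decreased | −8, Decreased | −10, Decreased |
| +3 | +3, Increased | +1, No Change | 0, No Change | −2, No Change | −5, Decreased | −7, Decreased |
| +5 | +5, Increased | +3, Increased | +2, No Change | 0, No Change | −3, Decreased | −5, Decreased |
| +8 | +8, Increased | +6, Increased | +5, Increased | +3, Increased | 0, No Change | −2, No Change |
| +10 | +10, Increased | +8, Increased | +7, Increased | +5, Increased | +2, No Change | 0, No Change |

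Every shift is towards the less favourable class. Large true rises survive a small under-reading; small true rises do not.

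**4. The lower cut-off as printed.** The middle category holds −2 ≤ *d* ≤ 2 and the lower one holds *d* < 2. Every value with −2 ≤ *d* < 2 therefore falls in both. Among whole numbers these are −2, −1, 0 and +1. A patient with *d* = 0 counts as Decreased even when *a* = 0. This error does not depend on the method of measurement, and correcting it does not cure the first problem.

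**5. After correction.** With a measure free of the artefact (*a* = 0) and a lower cut-off of < −2, true changes of 0, +3, +5, +8 and +10 are classed No Change, Increased, Increased, Increased and Increased. Each value falls in exactly one class.

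**The case against.** The strongest reply is that SpO₂ may be a loose label for the co-oximetry value in the protocol's vital-signs list, in which case the dye artefact does not arise. This cannot be excluded. The source would still be undefined and the name misleading, so the SAP needs a correction on either reading.

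A reader might infer that the SAP certainly analyses pulse oximetry and that a dye artefact is being counted as deterioration. The documents do not support that: the device is never stated, the label says only that under-reading may occur, and its size is not given. A reader might also infer that the sound measure has been discarded. It has not: co-oximetry saturation is profiled and listed, and only a categorical summary is missing. Mixing of two measures is likewise conditional, because the mapping rules belong to the Data Integration Plan, which is not among the documents.

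It is also fair to say that little depends on this display. Saturation is not among the efficacy endpoints in SAP 3.3.1 or protocol 7.2. No inferential statistics are planned, and no table title names SpO₂. The possible bias runs against the drug, so it cannot manufacture a favourable finding. These points limit the weight of the concern but do not remove it.

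Finally, co-oximetry specimens may be arterial or venous (SAP 5.1), and Table 5 puts SO₂ and SaO₂ in one row. Replacing SpO₂ without regard to specimen type could compare an arterial baseline with a venous follow-up. That stands, and the fix allows for it.

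**Conclusion.** The point holds as a defect of definition with a conditional bias. SAP 5.2.3 classifies a variable whose source is unstated, under a name that departs from the protocol's co-oximetry and suggests a method the label cautions against around infusion. If pulse-oximetry values are used, the threshold for Increased moves from a true rise above 2 to one above 2 + *a*, and a patient with no true change becomes Decreased once *a* exceeds 2. The size rests entirely on *a*, which the documents do not supply. The overlap of the two lower categories is certain and needs no assumption.

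The consequence is confined to one supportive descriptive summary. The primary endpoint uses metHb, which is obtained by co-oximetry, and is untouched. The correction should be made before the tables are produced, but no main conclusion of the report depends on it.

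**What to change.** In SAP 5.2.3 and Table 14.2.2.1:

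- State the source of the saturation value and which post-dose reading is classified.
- Base the three categories on co-oximetry or arterial saturation (SO₂/SaO₂ from Table 5). Compare baseline and post-dose values of the same specimen type only: arterial with arterial, venous with venous.
- Do not pool pulse-oximetry with co-oximetry values. Keep post-dose pulse-oximetry values in Listing 16.2.9, flagged as possibly affected by the dye.
- Correct the lower category to < −2.

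The OxyHb fraction is a weaker substitute, because it tends to rise as the metHb fraction falls and so partly repeats the primary endpoint.

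The cost is SAP wording and one derivation from fields the SAP already plans to hold in the laboratory domain. Patients with only pulse-oximetry readings, or without a same-specimen pair, drop out of this summary. Their number may not be small: registry sampling follows local practice, and the SAP records co-oximetry availability as a yes/no item. The table should report how many patients are left out.

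### SAP 5.2.3 sets the SpO2 class Decreased at <2 where its own ±2 rule implies < -2, so Decreased and No Change overlap (minor correction)

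*SAP*

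**What the plan says.** SAP 5.2.3 (Summaries of Vital Signs Change from Baseline) states that change in SpO2 "will be assessed in 3 categories, based on" a ±2% rule. It then lists the three classes, each using the same difference, postbaseline minus baseline:

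- Item 1: "Increased if the difference (postbaseline – baseline) is >2"
- Item 2: "No Change if the difference (postbaseline – baseline) is within ± 2"
- Item 3: "Decreased if the difference (postbaseline – baseline) is <2"

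No other section gives an SpO2 cut-off or says which class prevails when a value meets two. Table 4 in SAP 5.2.2 has normal ranges for blood pressure, respiratory rate and heart rate, but none for SpO2. The protocol records oxygen saturation among the vital signs (Section 15.2.2) without defining change classes. In any case, SAP Section 1 says that the SAP overrides the statistical sections of the protocols.

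**The concern.** A symmetric rule with No Change in the middle needs a lower cut-off of -2. The printed third cut-off is positive, so it reaches across zero and over almost the whole of the middle class. A patient whose saturation does not move, or rises by one point, satisfies the condition for Decreased.

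What is at stake is the reading of one table. The error can act in only one direction, by adding stable and slightly better patients to the class that signals worse oxygenation after treatment. The pool is small, so a few such patients would be visible in the percentages. Section 5.5 of the label (protocol Appendix 1) also warns that methylene blue can make pulse oximetry read low. To the extent that SpO2 values come from pulse oximetry, Decreased is a class that should not be inflated further by its definition.

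**Working it through.** **Inputs.** Let d be postbaseline minus baseline, in SpO2 points. From SAP 5.2.3, Increased is d > 2, No Change is -2 ≤ d ≤ 2 (reading within ±2 as inclusive), and Decreased is d < 2 as printed. The ±2% rule and item 2 together imply d < -2 for Decreased.

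**Overlap as printed.** The values meeting both items 2 and 3 satisfy -2 ≤ d ≤ 2 and d < 2, that is, -2 ≤ d < 2.

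| d | Increased | No Change | Decreased, printed (<2) | Decreased, implied (< -2) |
|---|---|---|---|---|
| -3 | no | no | yes | yes |
| -2 | no | yes | yes | no |
| -1 | no | yes | yes | no |
| 0 | no | yes | yes | no |
| +1 | no | yes | yes | no |
| +2 | no | yes | no | no |
| +3 | yes | no | no | no |

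Four of the five whole-number No Change values are in two classes; only +2 is in No Change alone. On a grid from -10 to +10 in steps of 0.1 (201 values), 40 values fall in two classes and none falls in no class. Increased overlaps with neither of the others.

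**With the implied cut-off.** On the same grid, with Decreased at d < -2, no value is in two classes and none is unclassified. The three classes partition the scale.

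**What each way of programming gives.**

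- Exclusive branches in the printed order (d > 2; otherwise within ±2; otherwise d < 2): only d < -2 reaches the third branch, so the intended classes result.
- Item 3 tested before item 2, as exclusive branches: everything below +2 becomes Decreased, and No Change keeps only d = 2 exactly.
- Item 3 coded on its own: the Decreased count includes every patient with -2 ≤ d < 2.
- Three independent flags: if k of n patients have -2 ≤ d < 2, the percentages add to 100 × (1 + k/n).

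**Size per patient.** SAP Section 1 gives enrolment of 7 and 24, so n is at most 7 + 24 = 31. One misclassified patient moves a percentage by at least 1/31 = 3.2 points. The step is larger in the efficacy analysis set if it is smaller: SAP 3.2 limits that set to Primary cases with metHb measured before and after infusion.

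The number of patients affected cannot be derived, because neither document gives a distribution of SpO2 changes.

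**The case against.** The strongest reply is that this is a slip whose meaning is plain from the lines around it. Three classes, a ±2% rule and a middle class of ±2 leave only one sensible lower cut-off, and a programmer who follows the printed order with exclusive branches obtains it without noticing the error. That stands. Miscounting is possible, but it is not a certain consequence of the text.

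The second reply concerns weight, and it also stands. SAP 3.3.1 lists metHb, three vital signs (blood pressure, respiratory rate and heart rate), and signs and symptoms; SpO2 is not among them. SAP 3.4 plans no inferential statistics, and SAP Section 4 expects mainly individual narratives. Listing 16.2.9 is to show vital signs and change from baseline by patient, so an odd classification could be traced. Blood-gas and co-oximetry saturation are handled separately in SAP 6.3.1.

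The third reply is that a minus sign may have been lost when the PDF was converted to text. This cannot be excluded, and there are character faults elsewhere, such as the oxygen content row of Table 5. But the ± signs and the dash survive in the same section, and the negative percent change in SAP 5.1.1 keeps its sign. The page itself should be checked.

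None of these replies makes item 3 correct as it reads. The SAP supplies no order of precedence, so the outcome is left to the programmer.

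A reader might go further and infer that the report will overstate deterioration in oxygenation, or that the efficacy conclusion is compromised. The documents do not support either inference. The first depends on how the items are coded, which is not stated. The second fails because no primary or secondary endpoint uses this classification.

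**Conclusion.** The definition is wrong as written. Decreased contradicts the section's own rule and overlaps No Change for all differences from -2 up to just under +2. The correction follows from the SAP's text alone and needs no clinical judgement.

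The point is minor. It affects one descriptive SpO2 summary in at most 31 patients and leaves the metHb and vital-sign endpoints unchanged. Whether any patient is miscounted depends on the code, and how many cannot be estimated from the documents.

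This rests on two assumptions: that the printed SAP page reads as the text does, and that within ±2 includes the end points. If the end points were excluded, the overlap would be -2 < d < 2, and a difference of exactly +2 would belong to no class. That is a further reason to state the boundaries explicitly.

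**What to change.** In SAP 5.2.3, item 3, replace <2 with < -2. State in item 2 that both end points are included, so that the classes read: Increased, d > 2; No Change, -2 ≤ d ≤ 2; Decreased, d < -2. Confirm that the table program uses these three conditions, and that the class counts add to the number of patients with both a baseline and a postbaseline SpO2 value.

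The cost is one minus sign and a short clarification in the SAP, plus a check of one line of code. No new data or additional analysis is required. If the table has already been produced, it need be rerun only if the program did not use these conditions.

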5.2.4. Individual Profiles of Vital Signs

The change from baseline in vital signs will also be graphically presented, showing the change by time (hours) for each patient (Figure 14.2.2.2), as illustrated in Figure 2: Example of Individual Profile of Blood Pressure Before and After Treatment and Figure 3. The profile will flag if the patient is a Primary case or a Secondary case.

Figure 2: Example of Individual Profile of Blood Pressure Before and After Treatment

[figure not shown]
[figure not shown]

Figure 3: Example of Individual Profile of Respiratory and Heart Rate Before and After Treatment

